9.3.4. Safety Analysis

All AEs will be coded using MedDRA. AEs will be categorized as oral and non-oral by the Medical Director or designee prior to database lock. AEs and oral soft tissue abnormalities will be listed by treatment and reviewed. Only treatment emergent AEs (i.e. those occurring after first use of either of the study treatments) will be tabulated. AEs occurring prior to randomisation will be included in the AE listing.

9.3.5. Repeatability Analysis

A number of subjects will have repeat gingivitis (MGI and TPI) assessments conducted by the examiner. The repeat assessments will be compared to the original assessments. The repeat assessments will not be used in any efficacy analysis. The purpose of repeated assessments is to check the consistency of the examiner. As each subject will provide around 100 records for repeatability judgement, one subject on the morning and one subject in the afternoon in each visit day over the course of the study is sufficient for repeatability assessment. The first and second assessments on each tooth at a given visit will be cross-tabulated and a weighted Kappa coefficient (κ) will be calculated, along with the 95% confidence interval, to assess the intra-examiner repeatability. Repeatability will be deemed [Fleiss]:

- Excellent, if $\kappa > 0.75$
- Fair to good, if $0.4 \leq \kappa \geq 0.75$
- Poor if $\kappa < 0.4$

All subjects who have repeatability data will be included in this analysis.

10. STUDY GOVERNANCE CONSIDERATIONS

10.1. Posting of Information on Publicly Available Clinical Trials Registers

Study information from this protocol will be posted on publicly available clinical trial registers before enrollment of subjects begins.

Document Name	207014 protocol	Document Identifier	Effective Date
Type	Version		
eldo_clinical_doc	5.0; Most-Recent; Effective; CURRENT	090032d580d1fee8	05-Apr-2017 13:38:03

10.2. Regulatory and Ethical Considerations, Including the Informed Consent

The study will be conducted in accordance with all applicable regulatory requirements, and with GSK policy.

The study will also be conducted in accordance with ICH Good Clinical Practice (GCP), all applicable subject privacy requirements, and the guiding principles of the current version of the Declaration of Helsinki. This includes, but is not limited to, the following:

- Before initiating a trial, the investigator/institution should have written and dated approval/favorable opinion from the IRB/IEC for the trial protocol (including amendments), written informed consent form, consent form updates, subject recruitment procedures (e.g., advertisements), investigator brochure/ safety statement (including any updates) and any other written information to be provided to subjects. A letter or certificate of approval will be sent by the investigator to the sponsor prior to initiation of the study, and also when subsequent amendments to the protocol are made.
- Signed informed consent to be obtained for each subject before participation in the study (and for amendments as applicable)
- Investigator reporting requirements (e.g. reporting of AEs/SAEs/protocol deviations to IRB/IEC)
- GSK will provide full details of the above procedures, either verbally, in writing, or both.

10.3. Quality Control (Study Monitoring)

In accordance with applicable regulations including GCP, and GSK procedures, GSK or designee (i.e. third party vendor) monitors will contact the site prior to the start of the study to review with the site staff the protocol, study requirements, and their responsibilities to satisfy regulatory, ethical, and GSK requirements.

When reviewing data collection procedures, the discussion will include identification, agreement and documentation of data items for which the CRF will serve as the source document.

GSK or designee will monitor the study and site activity to verify that the:

- Data are authentic, accurate, and complete.
- Safety and rights of subjects are being protected.
- Study is conducted in accordance with the currently approved protocol and any other study agreements, GCP, and all applicable regulatory requirements.

Document Name	207014 protocol		
Type	Version	Document Identifier	Effective Date
eldo_clinical_doc	5.0; Most-Recent; Effective; CURRENT	090032d580d1fee8	05-Apr-2017 13:38:03
Reason For Issue	Auto Issue		

The extent and nature of monitoring will be described in a written monitoring plan on file at GSKCH. The investigator (or designee) agrees to allow the monitor direct access to all relevant documents and agrees to co-operate with the monitor to ensure that any problems detected in the course of these monitoring visits are resolved.

10.4. Quality Assurance

To ensure compliance with GCP and all applicable regulatory requirements, GSK may conduct a quality assurance assessment and/or audit of the site records, and the regulatory agencies may conduct a regulatory inspection at any time during or after completion of the study.

In the event of an assessment, audit or inspection, the investigator (and institution) must agree to grant the advisor(s), auditor(s) and inspector(s) direct access to all relevant documents and to allocate their time and the time of their staff to discuss the conduct of the study, any findings/relevant issues and to implement any corrective and/or preventative actions to address any findings/issues identified.

The sponsor will be available to help investigators prepare for an inspection.

10.5. Conditions for Terminating the Study

Upon completion or premature discontinuation of the study, the GSKCH monitor will conduct site closure activities with the investigator or site staff, as appropriate, in accordance with applicable regulations including GCP, and GSKCH Standard Operating Procedures.

Both GSKCH and the Investigator reserve the right to temporarily suspend or prematurely discontinue this study at any time for reasons including, but not limited to, safety or ethical issues or severe non-compliance. For multicenter studies (if applicable), this can occur at one or more or at all sites.

If the trial is prematurely terminated or suspended for any reason, the investigator site should promptly inform the trial subjects and should assure appropriate therapy/follow-up for the subjects. Where required by the applicable regulatory requirements, GSKCH should inform the regulatory authority(ies).

In addition:

- If the investigator terminates or suspends a trial without prior agreement of GSKCH, the investigator site should promptly inform the sponsor and the IRB/IEC, and should provide the sponsor and the IRB/IEC a detailed written explanation of the termination or suspension.

Document Name	207014 protocol		
Type	Version	Document Identifier	Effective Date
eldo_clinical_doc	5.0; Most-Recent; Effective; CURRENT	090032d580d1fee8	05-Apr-2017 13:38:03
Reason For Issue	Auto Issue		

- If the GSKCH terminates or suspends a trial, the investigator should promptly inform the IRB/IEC and provide the IRB/IEC a detailed written explanation of the termination or suspension.
- If the IRB/IEC terminates or suspends its approval/favorable opinion of a trial, the investigator should promptly notify the GSKCH and provide GSKCH with a detailed written explanation of the termination or suspension.

10.6. Records Retention

Following closure of the study, the investigator must maintain all site study records (except for those required by local regulations to be maintained elsewhere), in a safe and secure location.

The records (study/ site master file) must be maintained to allow easy and timely retrieval, when needed (e.g., for a GSK audit or regulatory inspection) and must be available for review in conjunction with assessment of the facility, supporting systems, and relevant site staff.

Where permitted by local laws/regulations or institutional policy, some or all of these records can be maintained in a format other than hard copy (e.g., microfiche, scanned, electronic); however, caution needs to be exercised before such action is taken.

The investigator must ensure that all reproductions are legible and are a true and accurate copy of the original and meet accessibility and retrieval standards, including re-generating a hard copy, if required. Furthermore, the investigator must ensure there is an acceptable back-up of these reproductions and that an acceptable quality control process exists for making these reproductions.

The investigator must assure that the subject's anonymity will be maintained. On CRFs or other documents submitted to GSKCH, subjects should not be identified by their names or initials, but by an identification code. The investigator should keep a separate log of subjects' codes, names and addresses. Documents not for submission to GSKCH, e.g. subjects' written consent forms, should be maintained by the investigator in strict confidence.

GSK will inform the investigator of the time period for retaining these records to comply with all applicable regulatory requirements (GSKCH recommends that documents be kept for 10 years). The investigator is also required to keep subject identification codes on file for at least 15 years after completion or discontinuation of the study. The minimum retention time will meet the strictest standard applicable to that site for the study, as dictated by any institutional requirements or local laws or regulations, GSK standards/procedures, and/or institutional requirements.

Document Name	207014 protocol		
Type	Version	Document Identifier	Effective Date
eldo_clinical_doc	5.0; Most-Recent; Effective; CURRENT	090032d580d1fee8	05-Apr-2017 13:38:03
Reason For Issue		Auto Issue	

No study document should be destroyed without a prior written agreement between GSKCH and the investigator. The investigator must notify GSK of any changes in the archival arrangements, including, but not limited to, archival at an off-site facility or transfer of ownership of the records in the event the investigator is no longer associated with the site.

10.7. Provision of Study Results to Investigators, posting of Information on Publicly Available Clinical Trials Registers and Publication

Where required by applicable regulatory requirements, an investigator signatory will be identified for the approval of the clinical study report. The investigator will be provided reasonable access to statistical tables, figures, and relevant reports and will have the opportunity to review the complete study results at a GSK site or other mutually-agreeable location.

GSK will also provide the investigator with the full summary of the study results. The investigator is encouraged to share the summary results with the study subjects, as appropriate.

The procedures and timing for public disclosure of the results summary and for development of a manuscript for publication will be in accordance with GSK Policy.

A manuscript will be progressed for publication in the scientific literature if the results provide important scientific or medical knowledge.

Document Name	207014 protocol	Document Identifier	Effective Date
Type	Version		
eldo_clinical_doc	5.0; Most-Recent; Effective; CURRENT	090032d580d1fee8	05-Apr-2017 13:38:03

MLSI	MacPherson modification of the Lobene stain index
OHT	Oral Hard Tissue
OST	Oral Soft Tissue
PI	Plaque Index
PP	Per Protocol
RAP	Statistical Reporting and Analysis Plan
RLR	Review Listing Requirement
SAE	Serious Adverse Event
SD	Standard Deviation
SOC	System Organ Class
TEAE	Treatment Emergent Adverse Event

The purpose of this Statistical Reporting and Analysis Plan is to describe the planned analyzes and outputs to be included in the Clinical Study Report for Protocol 207014.

1 Summary of Key Protocol Information

This will be a single-centre, examiner-blind, randomized, stratified, two-treatment, parallel group clinical study in healthy adult volunteers with moderate gingivitis. Treatment effect will be determined by evaluating the efficacy, in a Chinese population, of a dentifrice containing 0.454% w/w stannous fluoride to control gingivitis and supra-gingival plaque following 6 and 12 weeks twice daily brushing, compared to a fluoride control dentifrice. During the 12 week treatment period, subjects will brush with their allocated study product twice daily.

General safety and tolerability will be assessed based on the frequency and severity of Adverse Events (AEs).

1.1 Study Design

This clinical study follows the study schedule below.

Procedure/Assessment	Visit 1	1 – 28 days between Visit 1 and Visit 2 ⁵	Visit 2 Week 0 (Day 0) ¹	Visit 3 Week 6 (Day 42+/- 3) ¹	Visit 4 Week 12 (Day 84+/- 3) ¹
	Screening		Baseline ¹	Week 6	Week 12
Informed consent	X				
Demographics	X				
Medical History ²	X				
Current / Concomitant medication	X		X	X	X
Urine pregnancy test ⁶			X	X	X
Oral soft and hard tissue (OST/OHT) examination ³	X				
Gross gingival assessment	X				
Inclusion/ Exclusion Criteria	X		X		
Subject Eligibility/ Continuance	X		X	X	X
Full OST examination			X	X	X
Modified Gingival Index (MGI),			X	X	X

Bleeding Index (BI) & Plaque Index (PI; disclosing)				
Stratification/ randomization			X	
Sub- & supra-gingival prophylaxis and flossing (with second clinician check after disclosing & residual plaque removal, if applicable i.e. confirmed plaque score of zero)			X	
Dispense study dentifrice, toothbrush, study instructions, diary & timer ⁴			X	X
Oral hygiene instruction review/ compliance checks including diary completion review			X	X
Supervised subject brushing at site			X	X
Collect study dentifrice, toothbrush & diary				X
Compliance checks including diary review				X
Optional dental prophylaxis				X
Adverse Events			X	X
Study Conclusion				X

¹ Subjects will abstain from overnight toothbrushing for a minimum of 12hrs (+6hr, -2hr) immediately prior to the assessment visits (Visits 2, 3 & 4).

² Including smoking status.

³ In relation to the general dentition exclusion criteria.

⁴ Timer only dispensed once, at visit 2 only.

⁵ Subjects will be instructed to brush using their normal toothpaste and following their normal routine between screening and baseline visits.

⁶ Female subjects of child bearing potential only.

1.2 Study Objectives

Objectives	Endpoints
Primary	
To compare gingivitis, as measured by BI, following twice daily use of an experimental 0.454% w/w stannous fluoride dentifrice compared to a fluoride control dentifrice after 12	Mean BI at 12 weeks.

weeks twice daily use.	
Secondary	
To compare gingivitis, as measured by the number of bleeding sites using BI, following twice daily use of an experimental 0.454% w/w stannous fluoride dentifrice compared to a fluoride control dentifrice after 12 weeks twice daily use.	Number of bleeding sites at 12 weeks.
To compare gingivitis, as measured by MGI, following twice daily use of an experimental 0.454% w/w stannous fluoride dentifrice compared to a fluoride control dentifrice after 12 weeks twice daily use.	Mean MGI at 12 weeks.
To compare dental plaque scores (PI; overall and interproximal) following twice daily use of an experimental 0.454% w/w stannous fluoride dentifrice to a fluoride control dentifrice after 12 weeks twice daily use.	Mean PI (overall and interproximal) at 12 weeks.
Other	
To compare gingivitis, as measured by BI, following twice daily use of an experimental 0.454% w/w stannous fluoride dentifrice compared to a fluoride control dentifrice after 12 weeks twice daily use.	Mean BI at 6 weeks.
To compare gingivitis, as measured by the number of bleeding sites using BI, following twice daily use of an experimental 0.454% w/w stannous fluoride dentifrice compared to a fluoride control dentifrice after 12 weeks twice daily use.	Number of bleeding sites at 6 weeks.
To compare gingivitis, as measured by MGI, following twice daily use of an experimental 0.454% w/w stannous fluoride dentifrice compared to a fluoride control dentifrice after 12 weeks twice daily use.	Mean MGI at 6 weeks.
To compare dental plaque scores (PI; overall and interproximal) following twice daily use of an experimental 0.454% w/w stannous fluoride dentifrice to a fluoride control dentifrice after 12 weeks twice daily use.	Mean PI (overall and interproximal) at 6 weeks.
To evaluate and compare MGI and BI in low (<2.00) and high (>2.00) MGI subgroups	Mean MGI & BI at 6 & 12 weeks (in subgroups).

following twice daily use of an experimental 0.454% w/w stannous fluoride dentifrice after 6 and 12 weeks twice daily use.	
To evaluate examiner MGI & PI measurement reproducibility for a random subset of the study population.	Kappa coefficient for MGI & PI

1.3 Treatments

	Test Product	Reference Product
Product Name	Experimental dentifrice containing 0.454% w/w stannous fluoride & 0.0721% w/w sodium fluoride (1450ppm fluoride in total)	Regular fluoride dentifrice containing 0.14% w/w sodium monofluorophosphate – Colgate® Triple Protection Dentifrice (1400ppm fluoride as sodium monofluorophosphate; SMFP)
Product Formulation Code (MFC)	CCI	Commercially Available (Chinese marketplace)
Dose	Full ribbon of dentifrice to cover the head of the study toothbrush provided	Full ribbon of dentifrice to cover the head of the study toothbrush provided

1.4 Sample Size Calculation

A sufficient number of subjects will be screened to randomize at least 120 subjects to ensure approximately 112 evaluable subjects complete the entire study (approximately 56 per treatment group).

With 56 subjects per treatment group, the study has at least 80% power to detect a treatment difference of 0.08 in bleeding index over a period of 12 weeks treatment. The standard deviation used in calculation is 0.14. The difference of 0.08 represents more than 15% improvement in the test dentifrice compared to the fluoride control dentifrice reference product. CCI

2 Planned Analyzes

2.1 Interim Analysis

No interim analysis is planned.

2.2 Final Analyzes

The final planned primary analyzes will be performed after the completion of the following sequential steps:

1. All subjects have completed the study as defined in the protocol.
2. All required database cleaning activities have been completed and database has been locked.
3. All criteria for unblinding the randomization codes have been met and the randomization codes have been distributed.

3 Considerations for Data Analyzes and Data Handling Conventions

3.1 Baseline Definition

For all endpoints the baseline value will be the latest pre-dose assessment with a non-missing value.

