- Subject eligibility / continuance
- Subjects will be instructed to brush using their normal toothpaste and following their normal routine between screening and baseline visits.

Visit 2 - Baseline Visit; Day 0

The following assessments will be conducted:

- Review of current/concomitant medications, adverse events
- Urine pregnancy testing will be carried out on all female subjects of child bearing potential.
- Full OST examination
- MGI
- BI
- PI (following plaque disclosure)
- Inclusion/exclusion criteria
- Subject eligibility / continuance
- Stratification/randomization
- Sub- & supra-gingival prophylaxis & flossing (with second clinician check after disclosing & residual plaque removal, if applicable)
- Confirmed plaque score of 0 by second clinician following dental prophylaxis.
- Dispense study dentifrice, toothbrush, study instructions, diary & timer
- Oral hygiene instruction review / compliance checks including diary completion review with subject
- Supervised subject brushing at site
- Adverse events

Visit 3 - Week 6; Day 42+-3

The following assessments will be conducted:

- Review of current/concomitant medications, adverse events
- Compliance checks including diary review
- Urine pregnancy testing will be carried out on all female subjects of child bearing potential.

Document Name	207014 protocol	Document Identifier	Effective Date
Type	Version		
eldo_clinical_doc	5.0; Most-Recent; Effective; CURRENT	090032d580d1fee8	05-Apr-2017 13:38:03

 • Subject eligibility / continuance • Full OST examination • MGI • BI • PI (following plaque disclosure) • Collect study dentifrice, toothbrush & diary • Dispense study dentifrice, toothbrush, study product usage instructions, diary & timer • Oral hygiene instruction review / compliance checks including diary completion review with subject • Supervised subject brushing at site • Adverse events
Visit 4 – Week 12; Day 84+/-3

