Type	Version		
eldo_clinical_doc	5.0; Most-Recent; Effective; CURRENT	090032d580d1fee8	05-Apr-2017 13:38:03

followed by a BI followed by dental plaque (PI) assessment (assessments must occur in the order written) for all teeth meeting the inclusion criteria. Following the MGI & BI assessments, and after rinsing with 20ml of water, subjects will rinse their mouth with disclosing solution before receiving a dental plaque assessment.

Eligible subjects will be stratified based on gender (male/ female), smoking status (yes/ no) and baseline mean overall MGI score (low: ≤ 2.00 ; high > 2.00) to ensure a balance in treatments across the strata, and then randomized into one of two treatment groups. Dental prophylaxis will be performed by a suitably qualified member of site staff for each subject using a standard dental prophylaxis paste followed by flossing by the examiner. Subject's teeth will be disclosed using a disclosing solution to check for residual plaque. A second clinician will check to ensure all plaque has been removed. Any residual plaque & calculus remaining will be removed by the second clinician by dental polishing with a standard dental prophylaxis paste, to bring the subject to a confirmed score of zero visible plaque (PI=0).

Following dental prophylaxis, subjects will receive their assigned study dentifrice, a diary, a toothbrush, a timer and instructions on product usage and diary completion. Subjects will brush their teeth with their allocated dentifrice, in their usual manner for one timed minute, under supervision. Subjects will continue to brush twice daily (morning and evening) for one timed minute recording each brushing on their study diary.

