After using the study dentifrice twice daily for one timed minute at home for 6 and 12 weeks, subjects will return to the study site (Visits 3 and 4, respectively) having abstained from oral hygiene for 12hrs (+6hr, -2hr) i.e. from overnight immediately before each assessment visit, if possible at approximately the same time of day as the baseline visit. The study dentifrice will be collected and the diary reviewed for treatment compliance. Pregnancy testing will be carried out on all female subjects of child bearing potential at each visit. Subjects will have a full OST examination and then undergo, in the following order, MGI, BI followed by PI assessments after disclosing. At Visit 3, subjects will receive another supply of assigned study toothpaste, a new toothbrush and diary. At Visit 4, subjects will return all study materials and have a dental prophylaxis if deemed appropriate by the investigator or examiner.

At Visits 2, 3, 4, repeatability data will be generated for MGI & PI assessments from replicate examinations on the same subject. Depending on subject visit scheduling, every effort will be made to complete one repeatability examination for each clinical measure during each clinical session, that is, one in the morning and one in the

Document Name	207014 protocol	Document Identifier	Effective Date
Type	Version		
eldo_clinical_doc	5.0; Most-Recent; Effective; CURRENT	090032d580d1fee8	05-Apr-2017 13:38:03

afternoon on each assessment day. Repeatability examinations will be separated by a minimum of 10 minutes and, where possible, separated by another subject. Replicate BI examinations will not be performed.

Visit 1 - Screening Visit

The following assessments will be conducted:

- Informed consent
- Demographics, medical history, current / concomitant medication, & smoking status.
- Urine pregnancy testing will be carried out on all female subjects of child bearing potential.
- Oral soft & hard tissue (OST/OHT)examination
- Gross gingival assessment
- Inclusion/exclusion criteria
- Subject eligibility / continuance
- Subjects will be instructed to brush using their normal toothpaste and following their normal routine between screening and baseline visits.

Visit 2 - Baseline Visit; Day 0

The following assessments will be conducted:

- Review of current/concomitant medications, adverse events
- Urine pregnancy testing will be carried out on all female subjects of child bearing potential.
- Full OST examination
- MGI
- BI

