6.2.4. Bleeding Index (BI) Assessment (Saxton, 1989)

The BI assesses the number of bleeding points elicited on probing as a measure of gingival condition. The gingivae will be air dried and then the examiner will use an Oulix color coded periodontal PCPII 5B Hufreidy or blunt-ended CPI probe to assess bleeding. The probe will be gently inserted into the gingival crevice to a depth of approximately 1 millimeter (mm) and then run around the tooth (at angle of ~ 60° to the long axis of the tooth), gently stretching the epithelium while sweeping from interproximal to interproximal along the sulcular epithelium. Minimum force should be used to avoid damage to the gingival tissue. The BI will be assessed on the facial and lingual gingival surfaces of each scorable tooth (7-7 in each arch). Three scores (according to the scale below) should be recorded buccally/labially (distal, body, mesial sites) and three scores lingually/palatally. All scorable teeth in one quadrant should be probed first (approximately 30 seconds) before recording the number of gingival units which bleed.

The BI scoring system will be as follows:

0 = no bleeding after 30 seconds

1 = bleeding upon probing after 30 seconds

2 = immediate bleeding observed

The BI will be assessed by the same examiner on all evaluable teeth at Baseline/Visit 2, Visit 3 and Visit 4.

Repeatability exercise will not be performed for BI. Due to the invasive nature of the BI assessment it is not feasible to conduct a repeatability exercise.

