6.2.6. Dental Prophylaxis

A suitable qualified member of clinical staff will provide professional dental prophylaxis for each subject using a standard prophylaxis polishing paste followed by flossing to ensure teeth are free of all supra and gingival calculus and plaque, both visually and by tactile assessment using a dental explorer. A second suitable qualified examiner will then visually check that all plaque has been removed following plaque disclosure. Subjects will have their plaque disclosed and any residual plaque remaining will be removed by the second clinician by dental polishing with a standard prophylaxis polishing paste to bring the subject to zero plaque.

In addition, at the final study visit, subjects will be offered a dental prophylaxis if determined appropriate in the opinion of the investigator or suitably clinically qualified designee.

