4.8 Analysis of Other Variables

A number of subjects will have repeated plaque index (PI) or gingivitis index (MGI) assessments conducted by the examiner. The repeat assessments will be compared to the original assessments separately for PI and MGI. The repeat assessments will not be used in any efficacy analysis. The first and second assessments on each tooth at a given visit will be cross-tabulated and a weighted Kappa coefficient (κ) will be calculated, along with the 95% confidence interval, to assess the intra-examiner repeatability ([Table 14.2.6](#) and [Table 14.2.7](#)). Repeatability will be deemed

- Excellent, if $\kappa > 0.75$
- Fair to good, if $0.4 \leq \kappa \leq 0.75$
- Poor if $\kappa < 0.4$

All subjects who have repeatability data will be included in this analysis. SAS PROC FREQ will be used for this analysis with codes similar to the following:

GlaxoSmithKline Consumer Healthcare Confidential

```
PROC FREQ DATA = INTRA;  
TABLES R1*R2/AGREE (wt = fc);  
RUN;
```

Where R1 = first assessment score by an assessor, R2 = second (repeat) assessment score by an assessor.

5 Changes to the Protocol Defined Statistical Analysis Plan

There is no change to the planned statistical analysis specified in the protocol version 5.0 [(Dated: 05/Apr/2017)].

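### Does the SAP's latest pre-dose baseline rule replace the Visit 2 scores with the zero-plaque check or a repeat examination?

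*SAP*

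**What the plan says.** SAP 3.1 defines baseline in one sentence: "For all endpoints the baseline value will be the latest pre-dose assessment with a non-missing value". SAP 3.3 adds that Visit 2 is baseline and counts as Day 0. The baseline score is then the covariate in the efficacy ANCOVAs (SAP 4.4.1.2, 4.5 and 4.6).

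The Visit 2 list in the protocol synopsis runs: MGI, BI, disclosed PI, randomization, prophylaxis, the item "Confirmed plaque score of 0 by second clinician following dental prophylaxis", dispensing, supervised brushing. Protocol 3.1 gives the same order, writes the result of the check as PI=0, and places product use afterwards: "Following dental prophylaxis, subjects will receive their assigned study dentifrice".

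Protocol 3.1 also provides for repeat examinations: "At Visits 2, 3, 4, repeatability data will be generated for MGI & PI assessments from replicate examinations on the same subject". For the bleeding index, Protocol 6.2.4 says "Repeatability exercise will not be performed for BI".

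**The concern.** The rule asks for the latest record before the first dose. MGI, BI and PI are not scored at screening, so the only choice is among Visit 2 records. For PI, the post-prophylaxis check is later than the efficacy examination, is still pre-dose and is described on the PI scale. For a subject in the Visit 2 repeatability exercise, the repeat MGI or PI is also later than the main examination. On a literal reading the rule could therefore take the wrong record in both cases.

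If it did, there would be four consequences:

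- Baseline plaque would be 0 for every subject. The covariate would then drop out of the overall and interproximal plaque models at Weeks 6 and 12.
- The plaque summaries by visit would show a baseline of 0 in a trial whose entry criterion is a mean PI of at least 1.5.
- The nonparametric fallback in SAP 4.4.1.3 analyses change from baseline. For plaque it would become an analysis of raw follow-up scores.
- Baseline MGI would come from the main examination in some subjects and from the repeat in others. It could then disagree with the stratum (cut at 2.00) used at randomization.

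**Working it through.** **The plan's own figure.** The concern disputes no stated number. For reference, the BI power statement (SAP 1.4) uses 56 per group, a difference of 0.08 and an SD of 0.14, with two-sided 0.05 from SAP 4.4:

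- SE = 0.14 × √(2/56) = 0.0265
- 0.08 / 0.0265 = 3.02, and 3.02 − 1.96 = 1.06, so power is 85.6% (85.0% with the noncentral t).

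This agrees with the stated minimum of 80%. The baseline question does not alter it, because BI has neither a repeat examination nor a post-prophylaxis score.

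**Repeat examinations.** SAP 4.8 states: "The repeat assessments will not be used in any efficacy analysis". Protocol 9.3.5 says the same. A covariate in an efficacy ANCOVA is part of that analysis, so the specific exclusion limits the general rule in SAP 3.1. Once repeats are removed, the latest pre-dose MGI is the main Visit 2 examination. Eligibility and the randomization stratum rest on that same examination, so they cannot diverge from baseline.

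**The zero-plaque check.** The two activities compare as follows.

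| | Efficacy PI | Post-prophylaxis check |
|---|---|---|
| Where described | Protocol 6.2.5; SAP 4.4.2.3 | Protocol 6.2.6, Dental Prophylaxis |
| Who | One study examiner, the same throughout | A second clinician |
| What is produced | Six site scores per tooth, averaged over all sites or over interproximal sites | Visual confirmation; residual plaque is polished away |
| Schedule of events | The MGI, BI and PI row | A parenthesis in the prophylaxis row, marked as if applicable |

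Protocol 6.2.6 describes the check this way: "A second suitable qualified examiner will then visually check that all plaque has been removed following plaque disclosure". It mentions no site scores and no interproximal mean. The check therefore does not produce the quantity that SAP 4.4.2.3 calls the overall or interproximal plaque score. Inclusion criterion 5c points the same way: it requires a mean PI of at least 1.5 at the baseline visit, which a baseline of 0 would contradict for every subject.

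**Size if the zero were nevertheless used.** A constant covariate explains nothing, so the SE of the treatment difference rises by 1/√(1 − ρ²). Here ρ is the within-group correlation of baseline and follow-up plaque. The documents do not give ρ, so 0.3 to 0.7 is an assumed range. The sample loss with the same effect on precision is ρ².

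| ρ (assumed) | SE factor | Equivalent sample loss | Simulated SE, Visit 2 baseline | Simulated SE, all-zero baseline |
|---|---|---|---|---|
| 0.3 | 1/√0.91 = 1.05 | 9% | 0.181 | 0.189 |
| 0.5 | 1/√0.75 = 1.15 | 25% | 0.164 | 0.188 |
| 0.7 | 1/√0.51 = 1.40 | 49% | 0.135 | 0.189 |

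The simulation used 112 subjects in two equal groups, within-group SD 1, a true difference of −0.50 and 2000 runs per row. The mean estimate was about −0.50 in every case, with either baseline. The loss would be one of precision, not of validity.

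**The case for a change.** The strongest reply is that SAP 3.1 is the only rule naming the baseline value, and that it covers all endpoints without exception. With no scoring before Visit 2, choosing the latest record can never help in this design: any record later than the main examination is the wrong one. The check appears under the Visit 2 heading for assessments, follows re-disclosure and is written as a PI value. The exclusion of repeats sits in a section on other variables, so a programmer must find it there and let it override SAP 3.1. One sentence would settle both matters at no cost in data or time.

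Part of this stands. SAP 3.1 does not name the Visit 2 record, and a clarifying sentence would do no harm. The rest is weaker. The Visit 2 list also contains dispensing and supervised brushing, so inclusion in it does not make an item an efficacy measurement. The exclusion of repeats is categorical and appears in both documents. An all-zero baseline would also be conspicuous: it would appear in the baseline rows of Tables 14.2.4.2 and 14.2.5.2, against an entry threshold of 1.5, and the ANCOVA would lose a rank. The remaining risk needs a case report form that stores the second clinician's confirmation as a PI record, and nothing in the documents shows that it does.

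**Conclusion.** The plan as a whole identifies the right baseline: the study examiner's main Visit 2 scores, made before randomization and prophylaxis. The repeatability part of the concern fails on explicit text in both documents. The zero-plaque part is a wording gap that analysts would fill sensibly, because the check does not yield the site scores from which the plaque endpoints are built.

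The primary BI analysis and the number of bleeding sites cannot be affected, and MGI is protected by the exclusion of repeats. At most the secondary (Week 12) and exploratory (Week 6) plaque comparisons are exposed. They would lose precision by a factor of 1.05 to 1.40 over the assumed correlation range, without bias, and only if the zero were stored as a PI record and then used. This conclusion rests on reading SAP 3.1 together with SAP 4.4.2.3 and 4.8 and Protocol 6.2.5, 6.2.6 and 9.3.5. No change is called for.
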